7.5 Reconstitution and Administration of CPI-613

CPI-613 must be diluted from 50 mg/mL to 12.5 mg/mL with 5% Dextrose Water or D5W (i.e., 1 portion of CPI-613 diluted with 3 portions of D5W) prior to administration. The diluted drug product should be visually inspected for clarity. If haziness, precipitate or coloration (other than colorless) is observed, do not use the diluted drug product for dosing. After dilution with sterile D5W, the solution is clear and has a pH of 8.4-8.8. The diluted CPI-613 drug product has been found to be stable for 24 hrs at room temperature and refrigeration temperature (Studies STA-010).

CPI-613 must be administered IV, via an IV catheter that is free flowing and free of air in the dead space of the IV catheter, to minimize vascular irritation, inflammation and acute toxicity of CPI-613 (Study NCL-049). Accidental co-administration of extra air in the dead space of IV catheters during administration of CPI-613 has demonstrated the potential to induce acute toxicity of CPI-613 according to animal studies (Study NCL-049). Also, accidental leakage of CPI-613 into the perivascular space during IV administration, which prolongs exposure of perivascular tissue to CPI-613, can induce significant local inflammation according to animal studies (Studies NCL-027 and NCL-030). To avoid local reactions at and around the site of administration, CPI-613 must be administered via a central venous catheter.

CPI-613 must not be administered as a bolus, but by infusion, at a rate of ~0.5 mL/min, via a central venous catheter with D5W running at a rate of about 125-150 mL/hr. This is to minimize potential acute toxicity of CPI-613, according to animal studies (Study NCL-049).

The following precautions must be taken when administering CPI-613:

- A. Confirmation of the placement of the IV line to ensure a lack of leakage of CPI-613 into the perivascular space.
- B. Confirmation that the IV line is free flowing.
- C. Confirmation that the IV line is free of dead air space.
- D. Dilute CPI-613 drug product with D5W, as instructed in the study protocol.
- E. Administer CPI-613 by infusion, not as a bolus.
- F. After administration of CPI-613, flush the IV line with ~10 mL of D5W to remove

Comprehensive Cancer Center of Wake Forest University
A Pilot Study: Open-Label Clinical Trial of CPI-613 in Patients with Advanced Bile Duct
Cancers
CCCWFU # 59212

residual CPI-613.

- G. To avoid local reactions at and around the site of administration, CPI-613 should be administered via a central venous catheter.

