5.0 STUDY PROCEDURES

Table 5-1 (below) provides an overview of the study procedures for the pre-study screen and pre-cycle 1 treatment period. The specifics are described in subsequent sections.

Table 5-1: Study Procedures for Pre-Study Screen and Pre-Cycle 1 Treatment Period

Assessments	Pre-Study Screen ⁸	Pre-Cycle 1 treatment (Given Only Once for Each Patient)	
		Days 1-5	Days 6-7
CPI-613 ¹		√	
Medical history	√		
Pregnancy test for women of child-bearing potential	√		
Evaluation of symptoms and vital signs	√ ³	√ ⁴	
ECOG performance status and survival	√		
Clinical chemistry, hematology and coagulation ²	√	√ ⁵	
Cardiac: Troponin I	√	√ ⁵	
Cardiac: ECG	√	√ ⁵	
CT w/ contrast (chest/abdomen/pelvis)	√		
CA-19-9	√		
Plasma CPI-613 concentrations, possibly metabolite concentrations, and possibly other analyses ⁶		√ ⁷	
Optional blood and serum samples ⁹	√		
Adverse event evaluation		√	√

ECOG = Eastern Cooperative Oncology Group; hr = hour; min = minute.

¹ CPI-613 is given as a 2-hr IV infusion via a central venous catheter.

² Specific chemistries are listed in section 5.2.2. Renal function will be assessed utilizing the Cockcroft-Gault formula. Coagulation (PT/PTT) will only be assessed at screening.

³ Other than evaluation of symptoms and vital signs, height and weight, physical exam, and medications are also determined during pre-study medical screening.

⁴ Perform on Days 1 and 4 only.

⁵ Perform on Days 1 and 5 only.

⁶ Obtained according to the following schedule: pre-dose (~5 min before dosing), and at 0.5, 1, 1.5, 2, and 4 hrs post-dose of CPI-613.

⁷ Day 1 only

⁸ Pre-study screening tests, which are also enrollment evaluations, must be performed according the following time frames:

Within 4 weeks: tumor assessment (CT w/ contrast), CA-19-9

Within 2 weeks: medical history, physical exam, vital signs, height, weight, ECG, ECOG, evaluation of symptoms and medications, clinical chemistry, hematology, coagulation, and troponin

Within 1 week: pregnancy test for women of child-bearing potential, pre-study labs and ECG obtained before enrollment may be used for Day 1

⁹ Optional blood and serum samples are for possible testing of biomarkers, predictors of biological responses, toxicity, genotype vs. drug response relationship, etc.

Comprehensive Cancer Center of Wake Forest University
A Pilot Study: Open-Label Clinical Trial of CPI-613 in Patients with Advanced Bile Duct Cancers
CCCWFU # 59212

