Table 5-2 (below) provides an overview of the study procedures for all treatment cycles and the follow-up period. The specifics are described in subsequent sections.

Table 5-2: Study Procedures for All Treatment Cycles and Follow-Up Period

Assessments	Cycles 1 and 2 (Each cycle is 4 weeks)								Cycles 3 through 12 (Each cycle is 4 weeks)								Follow-Up Every 2 months until death
	Week 1		Week 2		Week 3		Week 4		Week 1		Week 2		Week 3		Week 4		
	D1	D4	D1	D4	D1	D4	D3,4,or 5		D1	D4	D1	D4	D1	D4	D3, 4, or 5		
CPI-613 ¹	√	√	√	√	√	√			√	√	√	√	√	√			
Evaluation of symptoms and vital signs	√ ²		√ ²		√ ²				√ ²		√ ²		√ ²				
ECOG performance status and survival	√ ²		√ ²		√ ²				√ ²		√ ²		√ ²				
Clinical chemistry, hematology ^{2,3,9}	√ ²	√	√	√	√	√			√ ²								
Cardiac: Troponin I and ECG ⁹	√ ²								√ ²								
CT w/ contrast (chest/abdomen/pelvis)																√ ⁴	
CA-19-9																√ ⁴	
Plasma CPI-613 concentrations, possibly metabolite concentrations, and possibly other analyses ⁶	√ ⁸																
Optional blood and serum samples ¹⁰																√ ⁴	
Phone contact																√ ⁷	

ECOG = Eastern Cooperative Oncology Group; hr = hour; min = minute; D1 = day 1; D4 = day 4.

¹ CPI-613 is given as a 2-hr IV infusion via a central venous catheter. Treatment with CPI-613 may be adjusted +/- 1 day.

² These tests are performed with results available for review within 24 hrs before administration of the anti-tumor agents.

³ Specific chemistries are listed in section 5.2.2. Renal function will be assessed utilizing the Cockcroft-Gault formula.

⁴ Performed at the following time points: during week 4 (preferably Wednesday or later) of cycle 3 for all patients. For patients without progression, perform during week 4 of cycles 6, 9, and 12. In patients where progression was detected from the cycle 3 scan, perform during week 4 of cycle 5. If patient remains on study after cycle 5, perform every 3 months thereafter.

⁶ Plasma samples will be obtained pre-dose (~5 min before dosing), and at 0.5, 1, 1.5, 2, and 4 hrs post-dose of CPI-613.

⁷ Survival and post-study cancer treatment will be monitored bimonthly via telephone contact after the patients are taken off the trial.

⁸ Cycle 1 only

⁹ Within 1 week: pre-study labs and ECG obtained before enrollment may be used for Day 1

¹⁰ Optional blood and serum samples are for possible testing of biomarkers, predictors of biological responses, toxicity, genotype vs. drug response relationship, etc.

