6.0 TREATMENT WITH CPI-613

CPI-613 will be administered to patients as shown in Table 6-1 (below). Briefly, a treatment cycle is 4 weeks, with CPI-613 given on Days 1 and 4 of the first 3 weeks. CPI-613 will also be given for 5 consecutive days a week before the start of Cycle 1, and this Pre-Cycle 1 treatment will only be given once in each patient. During Pre-Cycle 1 and each treatment cycle, patients will be treated with CPI-613 at the same dose, unless dose modification is warranted (see Section 6.2).

Table 6-1: Administration of CPI-613 in Patients with Advanced Cholangiocarcinoma

Treatment Cycle			Administration of CPI-613
	Week	Day	
Pre-Cycle 1 (1 week)	1	1	2-hr IV infusion via a central venous catheter
		2	2-hr IV infusion via a central venous catheter
		3	2-hr IV infusion via a central venous catheter
		4	2-hr IV infusion via a central venous catheter
		5	2-hr IV infusion via a central venous catheter
Cycle 1 (4 weeks)	1	1	2-hr IV infusion via a central venous catheter
		4	2-hr IV infusion via a central venous catheter
	2	1	2-hr IV infusion via a central venous catheter
		4	2-hr IV infusion via a central venous catheter
	3	1	2-hr IV infusion via a central venous catheter
	4	2-hr IV infusion via a central venous catheter	
Cycle 2 (4 weeks)	1	1	2-hr IV infusion via a central venous catheter
		4	2-hr IV infusion via a central venous catheter
	2	1	2-hr IV infusion via a central venous catheter
		4	2-hr IV infusion via a central venous catheter
	3	1	2-hr IV infusion via a central venous catheter
	4	2-hr IV infusion via a central venous catheter	
Etc. up to a total of 12 cycles ^a			

hr = hour; IV = intravenous; min = minutes.

^a Additional cycles can be given if the investigator considers it beneficial to do so.

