7.3 Storage of CPI-613

CPI-613 should be stored under refrigeration, at 2°-8°C (36°-46°F), except when being prepared for administration.

7.4 Intravenous (IV) Infusion Sets, Syringes and IV Bags to be Used for Administration of CPI-613

CPI-613 must be administered IV by infusion, via an IV catheter with D5W running at a rate of about 125-150 mL/hr. To avoid local reactions at and around the site of administration, CPI-613 should be administered via a central venous catheter. Subsequent sections describe the appropriate types of IV catheters, IV bags, syringes and clinical solutions that can be used in mixing and administering CPI-613 to patients.

Leaching of Diethylhexyl Phthalate (DEHP): CPI-613 can cause leaching of DEHP from IV infusion sets and IV bags (Study COM-003). Therefore, DEHP-containing IV infusion sets, IV bags or syringes should not be used in mixing or administration of CPI-613. Examples of the IV sets, IV bags and syringes that do not contain DEHP and therefore can be used in the administration of CPI-613 are:

Extension Set for Syringe Pump Use: All extension sets from MED-RX do not contain DEHP.

Syringes: Kendall Monoject syringes, all mono-ject syringes are DEHP free.

IV Infusion Sets: A compatibility study has been conducted showing that CPI-613 is compatible with 4 commonly used IV infusion sets (Study# COM-001). Therefore, these 4 types of IV infusion sets, and IV infusion sets that are made with the same materials, can be used to administer CPI-613. These IV infusion sets are:

- PVC material - ADDitIV® Primary IV Set with Universal Spike, Backcheck Valve, 2 Injection Sites, DEHP-Free and Latex-Free, 15 drops/mL, REF V14453, B Braun Medical Inc.
- Latex material - Interlink® System Secondary Medication Set, 10 drops/mL, 2C7451, Baxter Healthcare Corporation
- PVC material - Surshield™ Safety Winged Infusion Set, 0.19 mL Volume, Latex-Free, DEHP-Free, SV*S25BLS, Terumo Medical Products Hangzhou Co. Ltd.
- Polyethylene material - Interlink® System Paclitaxel Set by Baxter HealthCare, Non DEHP-free: Polyethylene tubing with a 0.22 microfilter Item # 2C7558 10 drops/mL

Syringes: Compatibility studies (Studies# COM-001 and COM-002) have shown that CPI-613 drug product (50 mg/mL), and drug product diluted with D5W to various concentrations (1.6-25 mg/mL) are compatible with various types of syringes, as listed below. Therefore, any of these types of syringes, and syringes that are made with the

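### Section 7.5's infusion rate of about 0.5 mL/min delivers only 750 mg in 2 hours, so the required 2-hour infusion cannot be achieved at any planned cycle dose

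*Combined protocol and SAP*

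**What the plan says.** All the instructions are in the combined protocol and SAP.

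- **Concentration (Section 7.5):** "CPI-613 must be diluted from 50 mg/mL to 12.5 mg/mL with 5% Dextrose Water".
- **Rate (Section 7.5):** "CPI-613 must not be administered as a bolus, but by infusion, at a rate of ~0.5 mL/min, via a central venous catheter". The next sentence gives the reason: to limit acute toxicity seen in animal work (Study NCL-049). The precaution list in the same section repeats only "Administer CPI-613 by infusion, not as a bolus".
- **Carrier (Sections 7.4 and 7.5):** D5W runs in the line at 125-150 mL/hr. Section 7.4 puts it as "CPI-613 must be administered IV by infusion, via an IV catheter with D5W running at a rate of about 125-150 mL/hr".
- **Duration (Section 5.0):** footnote 1 of Tables 5-1 and 5-2 says "CPI-613 is given as a 2-hr IV infusion via a central venous catheter". Every dosing row of Table 6-1 in Section 6.0 says "2-hr IV infusion via a central venous catheter".
- **Dose (Sections 6.1.1 and 7.9):** the cycle dose is 2,300 mg/m² in Cohort 1, then 3,000 mg/m², or 1,700 mg/m² if 2,300 is not tolerated. Pre-Cycle 1 doses run from 600 to 3,000 mg/m²/day. The amount in mg is set by the patient's BSA.
- **Human experience (Section 6.1.2):** 3,000 mg/m² infused over 2 hours, twice weekly, is reported as the Phase I maximum tolerated dose (MTD), with no significant adverse effects at or below it.

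**The concern.** Concentration, rate and duration together fix the amount of drug delivered. Here that amount is far below any planned cycle dose, so staff must break either the stated rate or the 2-hour rule. No section scales the rate to the dose, extends the infusion or gives an order of precedence.

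Giving the dose in 2 hours departs severalfold from a rate that Section 7.5 presents as a protection against acute toxicity. Following the rate gives infusions of many hours, which the 2-hour Phase I MTD does not cover.

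Safety is a primary outcome, and escalation turns on one or two dose-limiting toxicities per cohort. If staff resolved the conflict differently from patient to patient, those counts would pool quite different exposures. Section 6.1.2 also justifies the starting dose by peak plasma concentration, which depends on infusion time. The last pharmacokinetic (PK) sample is at 4 hours; if that clock starts with the infusion, a slow infusion would still be running when the sample is drawn.

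**Working it through.** **Inputs.** Rate 0.5 mL/min and concentration 12.5 mg/mL (Section 7.5); duration 120 min (Tables 5-1, 5-2 and 6-1); doses 600 to 3,000 mg/m² (Section 6.1.1); mg = dose per m² × BSA (Section 7.9). The documents give no BSA distribution. I assume 1.8 m², with a range of 1.5 to 2.2 m².

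**Dilution.** One part drug to three parts D5W gives 50 / 4 = 12.5 mg/mL, so the protocol's concentration reproduces.

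**Amount delivered in 2 hours.** 0.5 mL/min × 120 min = 60 mL; 60 mL × 12.5 mg/mL = 750 mg.

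**Formulas**

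- Largest BSA that fits = 750 / dose
- Time at the stated rate (h) = dose × BSA / 12.5 / 0.5 / 60
- Rate needed for 2 hours (mL/min) = dose × BSA / 12.5 / 120

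Example at 3,000 mg/m² and 1.8 m²: 5,400 mg / 12.5 = 432 mL; 432 / 0.5 = 864 min = 14.4 h; 432 / 120 = 3.6 mL/min, which is 3.6 / 0.5 = 7.2 times the stated rate.

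| Dose (mg/m²) | Largest BSA (m²) | Hours at 0.5 mL/min, BSA 1.8 (1.5-2.2) | mL/min needed for 2 h, BSA 1.8 (1.5-2.2) | Multiple of stated rate at BSA 1.8 |
|---|---|---|---|---|
| 600 | 1.25 | 2.9 (2.4-3.5) | 0.72 (0.60-0.88) | 1.4 |
| 1,200 | 0.625 | 5.8 (4.8-7.0) | 1.44 (1.20-1.76) | 2.9 |
| 1,700 | 0.44 | 8.2 (6.8-10.0) | 2.04 (1.70-2.49) | 4.1 |
| 2,300 | 0.33 | 11.0 (9.2-13.5) | 2.76 (2.30-3.37) | 5.5 |
| 3,000 | 0.25 | 14.4 (12.0-17.6) | 3.60 (3.00-4.40) | 7.2 |

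**Could another reading rescue the text?**

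- *A generous reading of the approximation sign.* Doubling the rate to 1.0 mL/min delivers 1,500 mg in 2 hours. That fits up to 1.25 m² at 1,200 mg/m² and 0.88 m² at 1,700 mg/m².
- *0.5 mL/min of undiluted 50 mg/mL product.* This contradicts the mandatory dilution. It delivers 3,000 mg, enough up to 1.76, 1.30 and 1.00 m² at 1,700, 2,300 and 3,000 mg/m².
- *125-150 mL/hr as the drug rate.* The text assigns this flow to the D5W. At 12.5 mg/mL it would deliver 3,125-3,750 mg, enough up to 1.84-2.21, 1.36-1.63 and 1.04-1.25 m². At 1.8 m² it would fit 1,700 mg/m² (98-118 min) but not 2,300 (132-159 min) or 3,000 (173-207 min).
- *Dose reduction under Section 6.2.* Halving the lowest cycle dose gives 850 mg/m², which fits only up to 750 / 850 = 0.88 m².

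None of these makes the 3,000 mg/m² target deliverable in 2 hours anywhere in the assumed BSA range.

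**The case against.** The best counter-argument is that the governing rule can be inferred. Section 6.0 says the drug is given as Table 6-1 shows, and all its dosing rows specify 2 hours. Tables 5-1 and 5-2 and the MTD description in Section 6.1.2 agree. The rate appears once, in a section on preparation and handling. Its mandatory wording attaches most directly to the ban on bolus dosing, the rate itself is marked as approximate, and the reference list titles Study NCL-049 as a comparison of bolus with infusion in rats. A 2-hour infusion is not a bolus at any dose. On this view, staff would query the order and infuse over 2 hours, as in Phase I. No analysis or cohort rule uses the rate, so the harm would be a pharmacy query or a recorded deviation.

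Much of this stands. The 2-hour rule is the likelier intention, and Section 6.1.2 argues against treating the faster rate as a demonstrated hazard. But pointing to a table is not a precedence clause. An approximation sign cannot absorb a four- to sevenfold gap, and the toxicity rationale follows a sentence that contains the rate. What the animal study shows about rate cannot be checked from these documents. Staff who choose 2 hours are probably right, but they depart from a stated precaution at every cycle dose without written authority.

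**Conclusion.** The concern holds. The rate in Section 7.5 cannot be reconciled with a 2-hour infusion for any adult at 1,200 mg/m² or above, which includes every planned cycle dose. The 600 mg/m² fallback fits only up to 1.25 m².

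That conclusion rests on the 750 mg figure and not on the assumed BSA, since the limit at 1,200 mg/m² is already 0.625 m². Only the durations and rate multiples depend on the assumption: over 1.5 to 2.2 m², finishing in 2 hours needs 3.4 to 5.0 times the stated rate at 1,700 mg/m², 4.6 to 6.8 times at 2,300, and 6.0 to 8.8 times at 3,000.

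The rate is probably the wrong figure, but that is an inference for the sponsor to confirm. Because this is a dosing instruction tied to acute toxicity, it must be corrected.

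**What to change.** Have the sponsor confirm that the 2-hour infusion governs. Then replace the fixed rate in Section 7.5 with: infuse over 120 minutes; pump rate (mL/min) = dose in mg / 12.5 / 120. Keep the ban on bolus dosing. State also whether the D5W carrier continues at 125-150 mL/hr alongside the drug, because at 3,000 mg/m² and 1.8 m² the drug alone runs at 3.6 × 60 = 216 mL/hr.

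This costs one sponsor confirmation and a short amendment to Section 7.5, with no extra patients or procedures.

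If the sponsor instead keeps the slow rate, the cost is larger: the 2-hour entries in Tables 5-1, 5-2 and 6-1 must change, and the dose justification in Section 6.1.2 and the PK sampling times must be revisited.

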7.6 Request for CPI-613

CPI-613 must be requested from Cornerstone by the Principal Investigator (or authorized designees). CPI-613 may not be used outside the scope of this protocol, nor can it be transferred or licensed to any party not participating in this clinical study. Cornerstone policy requires that CPI-613 be shipped directly to the institution where the patient is to be treated. Cornerstone does not permit the transfer of CPI-613 between institutions (unless with prior written approval from Cornerstone). Requests must be submitted to Cornerstone by fax or email to the following address:

[name]
Department of Regulatory and Clinical Affairs
Cornerstone Pharmaceuticals, Inc.
[name]
[name]
[contact]
Telefax: [contact]
Email: [contact]

The following information must be provided in the request of CPI-613 from Cornerstone:

- Names of the principal investigator and the requestor (if different)
- Name of the study site
- Name of the pharmacist responsible for receiving and storing CPI-613
- Name of the person and address where CPI-613 is to be shipped to
- Amount (# vials) requested
- Date of request
- Date shipment expected
- Study Protocol (title and protocol#) for which the requested CPI-613 is to be used

7.7 Procurement of Investigational Drug

Relevant regulations require investigators to establish a record of the receipt, use and disposition of all investigational products. Investigators may delegate responsibility of drug ordering, storage, accountability and preparation to their designees.

The investigator, or the designee, will be responsible for dispensing and accounting of CPI-613 provided by Cornerstone and for exercising accepted medical and pharmacy practices.

Comprehensive Cancer Center of Wake Forest University
A Pilot Study: Open-Label Clinical Trial of CPI-613 in Patients with Advanced Bile Duct
Cancers
CCCWFU # 59212

Records of inventory, dispensation and disposition (vials received, source and dates) must be maintained. In addition, all doses dispensed should be accounted for by recording the date, study number and name, patient identification, patient initials, patient medical record number and balance forward. These records must be maintained and kept at the study site, and will be reviewed by Cornerstone, or its designee, during periodic monitoring visits.

7.8 Disposal of CPI-613

The following procedures are to be taken in disposal of CPI-613:

- During the study, store the used CPI-613 vials (which must be separate from the unused CPI-613 vials) at room temperature in an access-limited area. Alternatively, destroy the used CPI-613 vials according to institutional policy after documentation of the number of used CPI-613 vials and remaining volume in each used vial.
- At the end of the study, deface the label (both used and unused vials) with a permanent marking pen.
- For used CPI-613 vials (if not already destroyed according to institutional policy), after documentation of the number of used CPI-613 units and remaining volume in each container, the used containers should be destroyed at the site according to the institutional procedures for destroying toxic chemicals. A certificate documenting the destruction of used vials must be kept on file.
- All unused CPI-613 vials must be destroyed according to the policy of the institution. The destruction of CPI-613, and the quantity destroyed, must be documented. A copy of the Certificate of Destruction should be sent to:

[name]
Department of Regulatory and Clinical Affairs
Cornerstone Pharmaceuticals, Inc.
[name]
[name]
[contact]
Telefax: [contact]
Email: [contact]

7.9 Calculation of the Amount of CPI-613 for Each Patient

The amount of CPI-613 at each dose level is based on the BSA of the patient. The BSA values will be calculated based on the height and body weight taken during screening and this BSA value is used throughout the study. This is unless there is a >10% change in the body weight from baseline during the study. At that point, BSA should be revised based on the new body weight and height. The new BSA values will be used from that point on

Comprehensive Cancer Center of Wake Forest University
A Pilot Study: Open-Label Clinical Trial of CPI-613 in Patients with Advanced Bile Duct
Cancers
CCCWFU # 59212

for the remainder of the study, unless there is another >10% change in body weight which will require another revision of the BSA.

